12.3 Randomization and Stratification

Patients will be stratified by baseline dyspnea (0-7 versus 8+ for CDS total score) and assigned with equal probability to either RESPeRATE group or the control group using variable length permuted block randomization. Block sizes will be chosen randomly to ensure that future assignments cannot easily be inferred from previous ones. There will be no interim analyses for this pilot study, and analyses will not be done separately for each stratum.

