etc.) will be presented for each outcome measure at baseline and follow-up points stratified by treatment arm. Repeated measures (RM) ANCOVA models (fitted using PROC MIXED in SAS) will estimate the treatment effect for each outcome, test for treatment differences, and obtain adjusted post-treatment estimates of the variability of these outcomes. Estimates of outcome measure variability will be used to determine sample size for the subsequent trial. The primary RM ANCOVA model will include time, treatment arm, and the stratification factors. An unstructured covariance matrix will be used to account for the within-patient correlation over time. In secondary models, additional covariance structures (Toeplitz, Autoregressive, Compound Symmetry) will be assessed and the optimal structure will be chosen based on likelihood ratio tests for nested structures and the BIC statistic for non-nested structures. Least squares means and 95% confidence intervals will be provided for each outcome, stratified by treatment arm, and for the difference between treatment arms. Regression diagnostics and residual plots will be used to find appropriate transformations for variables in the model.

Subsequent RM ANCOVA models will include additional covariates (e.g., age, sex, stage) to correct for chance imbalances in important prognostic variables and account for variability in outcome measures due to covariates. These latter models will inform us of possible stratification factors for the subsequent trial. Limited exploratory analyses will be done to determine if the treatment effect differs for different levels of covariates (e.g., by including treatment by covariate interactions in the model) to see if the subsequent trial should be done in particular subsets of lung cancer survivors. It is likely that some data will be missing. In addition to the mixed models above, we will use multiple imputation pattern-mixture models under various assumptions (e.g., participants in the active arms who drop out would have subsequent patterns similar to participants in the control arm) to assess the sensitivity of our modeling assumptions.

The optimal dose will be defined as the one that results in the greatest improvement in anxiety scores at 12 weeks (based on estimates from the RM ANCOVA model). This dose will be used in the subsequent trial, assuming that it is one of the RESPeRATE intervention groups.

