12.5 Secondary Endpoint(s)

Epigenetic and Gene Expression Analyses.

To characterize the DNA methylation and gene expression patterns between the different groups, mixed effects models will be used. Changes of methylation or expression levels will be treated as the dependent variables and the intervention groups will be the independent variable of interest. Baseline methylation or expression levels, age, chip, chip position, and other covariates will be adjusted in the model. After comparing the fit of these data at a set of 20 random CpG markers (for the methylation analysis only), the alternative paired difference between baseline and twelve weeks (percent change dividing the difference by baseline value) will be examined to see if it provides a better fit to these data.

To determine if changes in anxiety are associated with methylation or gene expression patterns, mixed effects models will be used, and changes in anxiety variables will be treated as the dependent variables. Baseline methylation or expression, change of methylation or expression,

intervention group, and interaction between intervention group and change of methylation or expression will be included in the model, along with the appropriate covariates. If the interaction effect is significant, it means that the association between the change in anxiety and change in methylation or expression proportion is not the same between the two exposure groups. Multiple comparisons will be adjusted using Bonferroni correction as before.

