Salivary Cortisol Analyses. Participants with endocrine disorders (e.g., diabetes and thyroid disorders) or on steroid-based medications are excluded from the cortisol portion of the study (topical hydrocortisone cream permitted). Cortisol levels will be assessed upon awakening, 30 minutes post-awakening, and at bedtime for three consecutive days at baseline and three consecutive days at 12 weeks. Several measures will be derived from the three daily cortisol values, including the mean levels at each time, the mean cortisol awakening response (CAR – change in cortisol from awakening to 30 minutes), the area under the curve (AUC), and the diurnal slope (change in cortisol between awakening and bedtime). Scatterplots and correlations will be used to quantitate the associations between these measures, and anxiety at each time (baseline and 12 weeks) as well as association between the change in cortisol measures and the change in anxiety. Additionally, mixed effects models, as described above, will be used to assess the association between baseline cortisol and changes in anxiety over time. To assess group differences in cortisol parameters, each of these measures at 12 weeks will be used as dependent variables in analysis of covariance models, using appropriate transformations as needed. Baseline levels of the measures will be used as covariates along with treatment group.

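### The cortisol ANCOVA omits the dyspnea stratum used at randomisation, and no arm handling is specified for the 12-week and change correlations between cortisol and anxiety

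*Combined protocol and SAP*

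**What the plan says.** **Group comparison.** In the cortisol part of Section 12.5, "each of these measures at 12 weeks will be used as dependent variables in analysis of covariance models". The only terms named are in the next sentence: "Baseline levels of the measures will be used as covariates along with treatment group". There is no open-ended covariate clause of the kind the genomic models in the same section have.

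**Randomisation and primary model.** Sections 6.4.2 and 12.3 stratify by Cancer Dyspnea Scale total (0-7 against 8 or more). Section 12.4 says "The primary RM ANCOVA model will include time, treatment arm, and the stratification factors".

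**Associations with anxiety.** Section 12.5 plans plots and correlations of the cortisol measures with anxiety, at baseline and at 12 weeks. It extends this to change scores: "as well as association between the change in cortisol measures and the change in anxiety". These analyses are split by time point only. Mixed models carried over from earlier in the plan are also promised, but they "will be used to assess the association between baseline cortisol and changes in anxiety over time", so they do not cover 12-week cortisol or its change.

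**Parallel genomic analysis.** For change in anxiety against change in methylation or expression, Section 12.5 says that "intervention group, and interaction between intervention group and change of methylation or expression will be included in the model".

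**Purpose.** Objective 1.5 is supplemental. It seeks preliminary data on cortisol changes in each group and on the association of cortisol with anxiety. Section 2.1c hypothesises that anxiety changes attributed to the device go together with changes in cortisol response.

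**The concern.** There are two separate gaps.

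First, when randomisation is balanced on a factor related to the outcome, an analysis that leaves the factor out counts its variation as residual noise. The arm estimates have already been protected from that variation, so the reported standard errors are larger than they should be. The cortisol subset is smaller than the 75 randomised, because participants with endocrine disorders or on steroid-based medication are excluded, so precision is worth keeping.

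Second, after randomisation the arms may differ in mean anxiety and in mean cortisol. A correlation over all arms then combines two things: whether people with lower cortisol also have lower anxiety within an arm, and whether the arm means move together. The second can occur without the first. The baseline correlation is not affected, because it precedes treatment.

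**Working it through.** **Planning figures in Section 12.2.** Three normal arm means with SD 1, true means 0, -0.5 and -1.0, 20 per arm and 200,000 repetitions give a probability of 0.902 that the high-dose arm is chosen and lies at least 0.5 SD below control (stated: 90%). With no effect, the probability of stopping is 1 - 0.098 = 0.902 (stated: 90%). Accrual is 60/0.8 = 75. The plan's figures reproduce, and its anxiety means are used below.

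**A. Gain from adding the stratum**

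Assumptions, none of them in the documents: the stratum has correlation a with both baseline and week-12 cortisol (0.1-0.3), and these two have correlation ρ (0.3-0.7). Baseline cortisol is already in the model, so the share of residual variance removed is the squared partial correlation:

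a²(1 - ρ) / [(1 - a²)(1 + ρ)]

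- a = 0.1, ρ = 0.7: 0.01 × 0.3 / (0.99 × 1.7) = 0.0018, or 0.2%
- a = 0.1, ρ = 0.5: 0.01 × 0.5 / (0.99 × 1.5) = 0.0034, or 0.3%
- a = 0.3, ρ = 0.5: 0.09 × 0.5 / (0.91 × 1.5) = 0.033, or 3.3%
- a = 0.3, ρ = 0.3: 0.09 × 0.7 / (0.91 × 1.3) = 0.053, or 5.3%

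As a standard-error ratio, 1/√(1 - 0.0018) = 1.001 and 1/√(1 - 0.053) = 1.028. Without the stratum the standard error is therefore about 0.1% to 2.8% too large.

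Simulation under stratified permuted blocks checks the direction. It used 20 per arm, 6,000 repetitions, half the participants in each stratum, residual variance 0.75 given baseline, and a stratum unrelated to baseline cortisol:

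| Stratum difference b in week-12 cortisol (SD) | Residual variance due to stratum, 0.25b²/(0.75 + 0.25b²) | SE without / with stratum | Type I error without | with |
|---|---|---|---|---|
| 0.3 | 2.9% | 1.015 | 4.6% | 4.9% |
| 0.6 | 10.7% | 1.06 | 3.6% | 4.8% |
| 1.0 | 25% | 1.16 | 2.5% | 4.9% |

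Monte Carlo error is about √(0.05 × 0.95/6000) = 0.3 percentage points. Only the first row falls inside the 0.2-5% range; the other two show what a much stronger stratum effect would do. The error is on the conservative side throughout.

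**B. Correlation produced by arm differences alone**

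The anxiety means 0, -0.5 and -1.0 in equal arms have between-arm variance v = (0.25 + 0 + 0.25)/3 = 1/6. Let the cortisol arm effects be k times the anxiety effects (k is assumed; no document gives it), with unit within-arm variances and zero within-arm correlation. The overall correlation at 12 weeks is

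r = kv / √[(1 + v)(1 + k²v)]

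- k = 1: 0.1667/1.1667 = 0.14
- k = 0.5: 0.0833/√(1.1667 × 1.0417) = 0.08
- k = 0: 0
- k = -1: -0.14

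If a nominal 5% test were applied at 20 per arm, it would reject in 19% (k = 1), 9% (k = 0.5) and 5% (k = 0) of trials. The cortisol subset size is not stated; for k = 1 the rate is 13% at 12 per arm, 17% at 16 and 23% at 25.

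For change scores with k = 1, divide v by the change-score variance 2(1 - ρ), with the same ρ assumed for both measures:

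- ρ = 0.3: v = 0.1667/1.4 = 0.119, r = 0.119/1.119 = 0.11, rejection 13%
- ρ = 0.5: v = 0.1667/1.0 = 0.167, r = 0.14, rejection 19%
- ρ = 0.7: v = 0.1667/0.6 = 0.278, r = 0.278/1.278 = 0.22, rejection 40%

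Adjusted for arm, the mean correlation is 0.00 and rejection about 5% in every scenario.

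**The case against.** **The plan does not say the correlations are pooled.** This stands. A reader might infer pooling from the missing arm term, but Section 12.5 does not say whether the correlations are overall, by arm or adjusted. What the text supports is that arm handling is unspecified.

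**The unadjusted correlation is not wrong in itself.** This also stands. A reader might take objective 1.5 to ask for a within-person association, which the unadjusted analysis would miss. The objective asks only for associations, and an arm-adjusted correlation is still a between-person, within-arm quantity. Section 2.1c includes co-movement attributed to the device, and adjustment for arm removes the between-arm part of it. This argues for reporting both results, not for replacing one with the other.

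**Section 12.4 sets no rule for supplemental models.** Correct. It governs the primary model, so the cortisol ANCOVA is less complete but does not contradict it.

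**The sizes rest on assumed effects.** True, hence the ranges. Squaring correlations of 0.1-0.3 would suggest a 1-9% gain from the stratum, but that ignores the baseline cortisol already in the model. The sign in part B is also not fixed: the awakening response and diurnal slope are differences, and a device effect on them need not run in the same direction as its effect on anxiety.

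**Little depends on it.** No test or decision rule is attached to these correlations, and arm differences in cortisol are reported anyway. It would go too far to say that a spurious link will be reported as a finding. The gap remains, however, because the parallel genomic model includes arm and nothing in the plan explains the difference.

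**Conclusion.** The point holds in a limited form.

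- **Stratum.** It is missing from the cortisol ANCOVA. A reader might infer bias or excess false positives; neither follows. The arm comparison stays unbiased as far as this omission goes, the intervals are somewhat too wide and the test is conservative. The gain from adding the stratum is about 0.2-5% of residual variance under the assumed correlations, and close to nothing at the lower end.
- **Correlations.** Arm handling is unspecified for the 12-week and change associations. If they are computed over all arms, arm effects on both measures can produce a correlation without any within-arm association. With the plan's anxiety means, its size at 12 weeks is 0.14, 0.08 or 0 for a cortisol effect equal to, half of, or absent relative to the anxiety effect, with the sign depending on the cortisol measure. If the device does not affect cortisol there is no distortion.

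Only a supplemental, preliminary objective is touched. Dose selection and sample size do not use these results. Label: free improvement.

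**What to change.** 1. In the cortisol ANCOVA of Section 12.5, add the dyspnea stratum (0-7 against 8 or more) to the baseline measure and treatment group. Cost: 1 df. The score is already collected, because it is required for registration.
2. For the 12-week and change associations, state that the unadjusted correlation and an arm-adjusted one (partial correlation, or regression with an arm term) will be reported side by side, and that scatterplots will be marked by arm. Say which result addresses the within-arm association and which also includes device-driven co-movement. Cost: 2 df for arm in the adjusted version, for example 58 to 56 df with 60 participants.
3. In the same edit, define the stratification factors once. The Schema lists site as well as dyspnea, while Sections 6.4.2 and 12.3 list dyspnea only. The 1 df above is for dyspnea alone.

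These are wording changes to the analysis plan and need no new data.

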12.6 Reporting and Exclusions

An objective of this study is to estimate adherence and retention as defined above in Section 12.4. Note that all participants will be included in all primary analyses, regardless of adherence or retention using all data that have been collected. Secondary analyses will be conducted using those participants who were at least 75% adherent to see if the “per protocol analysis” gives similar results as the “intent-to-treat analysis.”

12.7 Evaluation of Toxicity

All participants will be evaluable for serious adverse events from the time of their randomization. Toxicities will be evaluated using the NCI Common Terminology Criteria for Adverse Events (CTCAE) version 4.03. Fisher exact tests will be used to assess differences in toxicity rates between the three arms.

12.8 Evaluation of Response

Tumor response is not an outcome. Response for this study will be the change in anxiety from baseline to 12 weeks, and this outcome will be assessed in all participants. Analysis of this outcome is described above in Section 12.4.

12.9 Interim Analysis

There will be no formal stopping rules based on interim analyses for this pilot study. However, all Research Base studies are reviewed by the DSMB every six months so the data from this study will be reviewed on that schedule. The report completed for the DSMB includes a summary of accrual, adherence, and retention, descriptive statistics for baseline characteristics and patient status, descriptions of all adverse events and toxicities, estimates of data completeness, a summary of the primary and secondary outcome measures.

Reference List

2. The National Lung Screening Trial Research Team. Reduced Lung-Cancer Mortality with Low-Dose Computed Tomographic Screening. 2011;365(5):395-409
8. Jacobsen PB DKSZetal. Management of anxiety and depression in adult cancer patients: Toward an evidence-based approach. In: Chang AE GPHDea, editor. *Oncology: An Evidence-Based Approach*. Philadelphia, PA: Springer; 2006. p. 1552-79.
